	24					
	36					
	48					
	Mean (SE) difference from baseline to week 48					
Alkaline phosphatase (U/L)	0					
	4					
	8					
	12					
	24					
	36					
	48					
	Mean (SE) difference from baseline to week 48					
Creatinine phosphokinase (U/L)	0					
	4					
	8					
	12					
	24					
	36					
	48					
	Mean (SE) difference from baseline to week 48					
Calcium (mmol/L)	0					
	4					
	8					
	12					
	24					
	36					
	48					

	Mean (SE) difference from baseline to week 48					
Urea (mmol/L)	0					
	4					
	8					
	12					
	24					
	36					
	48					
	Mean (SE) difference from baseline to week 48					
Phosphate (mmol/L)	0					
	4					
	8					
	12					
	24					
	36					
	48					
	Mean (SE) difference from baseline to week 48					
Chloride (mmol/L)	0					
	4					
	8					
	12					
	24					
	36					
	48					
	Mean (SE) difference from baseline to week 48					
Total cholesterol (mmol/L)	0					
	4					
	8					

	12					
	24					
	36					
	48					
	Mean (SE) difference from baseline to week 48					
HDL (mmol/L)	0					
	4					
	8					
	12					
	24					
	36					
	48					
	Mean (SE) difference from baseline to week 48					
LDL (mmol/L)	0					
	4					
	8					
	12					
	24					
	36					
	48					
	Mean (SE) difference from baseline to week 48					
Triglycerides (mmol/L)	0					
	4					
	8					
	12					
	24					
	36					
	48					
	Mean (SE) difference from baseline to week 48					

Glucose (mmol/L)	0					
	4					
	8					
	12					
	24					
	36					
	48					
	Mean (SE) difference from baseline to week 48					

The mean change in laboratory parameters from baseline to week 48 will be compared between the 2 treatment groups using a mixed model with random intercept and slope and spatial power covariance structure due to unequal time intervals between visits.

TABLE 16: CHANGE FROM BASELINE IN URINE PARAMETERS

Urine parameters	Week	Integrase Inhibitor N=xxx		Protease Inhibitor N=xxx		P-value between groups
Creatinine (mmol/L)	0					
	4					
	8					
	12					
	24					
	36					
	48					
	Mean (SE) difference from baseline to week 48					
Glucose (mmol/L)	0					
	4					
	8					
	12					
	24					
	36					
	48					
	Mean (SE) difference from baseline to week 48					
Positive/trace Glucose Dipstick, n (%)	0					
	4					
	8					
	12					
	24					
	36					
	48					
	Relative risk (RR, 95% CI) from baseline to week 48					
Proteins (mg/L)	0					
	4					
	8					
	12					

	24					
	36					
	48					
	Mean (SE) difference from baseline to week 48					
Albumin (mg/L)	0					
	4					
	8					
	12					
	24					
	36					
	48					
	Mean (SE) difference from baseline to week 48					
Albumin : Creatinine ratio (ACR) (mg/mmol)	0					
	4					
	8					
	12					
	24					
	36					
	48					
	Mean (SE) difference from baseline to week 48					
Protein : Creatinine ratio (PCR) (mg/mmol)	0					
	4					
	8					
	12					
	24					
	36					
	48					
	Mean (SE) difference from baseline to week 48					
Phosphate (mmol/L)	0					
	4					

	8					
	12					
	24					
	36					
	48					
	Mean (SE) difference from baseline to week 48					
Beta-2 microglobulin (mg/L)	0					
	4					
	8					
	12					
	24					
	36					
	48					
	Mean (SE) difference from baseline to week 48					
Positive Leukocytes, n (%)	0					
	4					
	8					
	12					
	24					
	36					
	48					
	Relative risk (RR, 95% CI) from baseline to week 48					

The change in continuous urine parameters from baseline to week 48 will be compared between the 2 treatment groups using a mixed model with random intercept and slope and spatial power covariance structure due to unequal time intervals between visits.

Change in binary parameters from baseline to week 48 will be compared between the 2 treatment groups using a Generalised Estimating Equation (GEE) with independent covariance structure, binomial distribution and log link.

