7.2 SECONDARY EFFICACY ANALYSES

7.2.1 Cumulative incidence of the composite primary endpoint

Endpoint

Cumulative incidence of the composite primary endpoint. All the observed events for each patient over the total duration of follow-up will be considered. Patients with multiple events on a given day will be considered as having one event on that day. For virological events only first episode was considered and data were censored at the time of treatment discontinuation.

Descriptive statistics and graphical representation

The cumulative incidence of the primary composite endpoint will be summarized with the total number of events, person-years, and the incidence rates per 100 person-years by treatment group (Integrase inhibitor versus Protease inhibitor).

Statistical methodology

In this analysis, the event is the sum of all episodes of the composite primary endpoint. For this analysis, the entire follow-up will be considered (i.e. follow-up will begin at baseline and continue until the 48-week visit, study discontinuation, loss to follow-up; whichever occurs first). All participants will be censored on the date of their last observation.

The cumulative incidence of the composite primary endpoint will be estimated by the total number of events divided by the total number of person-years of observation. The person-year is the total sum of the number of years that each subject of the study population has been under observation. The number of years each subject would have been under observation will be calculated by the difference between the date of the last observation and the date of study treatment initiation plus one, divided by 365.25.

The effect of study treatment will be assessed using a Poisson regression model adjusted for the stratification factor (country/group of neighbouring countries and baseline CD4 cell counts (<50 or $\geq50/\mu\text{L}$)). An adjusted incidence rate ratio (IRR) and the associated 95% CI will be calculated.

All P-values will be two-tailed with a significant level at 5%.

This analysis will only be performed if it is added additional information: i.e. if the number of cumulative episodes is greater than that of the first episode (with at least 10 additional events).

7.2.2 HIV-RNA viral load <50 copies/mL at week 24, 36 and 48

Endpoint

The proportion of patients with HIV-RNA viral load <50 copies/mL at week 24, 36 and 48 using the snapshot approach.

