Resistance to 3TC/FTC (stanford algorithm)				
	Resistance			
	Intermediate			
	Sensitive			
Resistance to TAF (stanford algorithm)				
	Resistance			
	Intermediate			
	Sensitive			
Resistance to TDF (stanford algorithm)				
	Resistance			
	Intermediate			
	Sensitive			

TABLE 2. PRIMARY COMPOSITE ENDPOINT AND ITS COMPONENT

	mITT analysis			PP analysis		
	Integrase Inhibitor	Protease Inhibitor	Adjusted Hazard ratio	Integrase Inhibitor	Protease Inhibitor	Adjusted Hazard ratio
	N=XXX	N=XXX		N=XXX	N=XXX	
Primary composite endpoint						
Virological failure						
Insufficient virological response						
Viral rebound						
Clinical events						
Any new or recurrent AIDS defining event on, or after 28 days of therapy						
SAE due to Non-AIDS events						
AE leading to discontinuation						
Death						

Insufficient virologic response: (HIV-1 RNA reduction < 1 log 10 copies/mL at week 12, or Viral load > 50 HIV-1 RNA copies/mL at week 48).

Viral rebound: confirmed rebound of HIV-1 RNA to >200 copies/mL after having achieved HIV-1 RNA <50 copies/mL, or confirmed rebound of HIV RNA by >1 log 10 copies/mL from nadir value, for patients whose viral load has never been suppressed below 50 copies/mL.

TABLE 2B. CUMULATIVE INCIDENCE OF THE PRIMARY COMPOSITE ENDPOINT

	Integrase Inhibitor (N=xxx)			Protease Inhibitor (N=xxx)			Adjusted Incidence	
	N of event	Person- years	IR per 100 p-y	N of event	Person- years	IR per 100 p-y)	rate ratio (95% CI)	p- value
Composite Primary endpoint								

All observed endpoint will be considered in the analysis. In this analysis, the entire follow-up will be considered (i.e. follow-up began at baseline and continued until the end of the study, study discontinuation, loss to follow-up; whichever occurs first). The incidence rates will be calculated by the total number of events from baseline to the end of the study divided by the total number of person-years. The incidence rates will be compared between the treatment groups (Integrase inhibitor versus Protease inhibitor) with a Poisson regression model adjusted for stratification factor. The incidence rates ratio and the associated 95% confidence interval will be calculated.

TABLE 3. HIV-RNA VIRAL LOAD <50 COPIES/ML AT WEEK 24, 36 AND 48

		Integrase Inhibitor		Protease Inhibitor		Adjusted OR	adjusted difference
		N=XXX		N=XXX		(95% CI)	(95% CI)
		N	% (95% CI)	N	% (95% CI)		
W24	HIV-RNA < 50 copies/mL						
	HIV-RNA ≥ 50 copies/mL						
	Data in window not below 50 copies/mL						

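### The total-event rate of the primary composite has two different end dates (SAP 7.2.1 and Table 2B), and its person-years run on where virological events no longer count

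*Combined protocol and SAP*

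**What the plan says.** The analysis is the SAP's first-listed secondary endpoint, labelled in SAP 2.2.2 as assessed at week 48. It counts all episodes of the composite rather than the first only. It is run only if there are at least 10 more events than first episodes.

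**End of follow-up.** SAP 7.2.1: "follow-up will begin at baseline and continue until the 48-week visit, study discontinuation, loss to follow-up; whichever occurs first". The Table 2B footnote: "follow-up began at baseline and continued until the end of the study, study discontinuation, loss to follow-up; whichever occurs first", with a numerator defined as the "total number of events from baseline to the end of the study divided by the total number of person-years".

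**Person-time.** In 7.2.1 the rate "will be estimated by the total number of events divided by the total number of person-years of observation". Each subject's time is the "difference between the date of the last observation and the date of study treatment initiation plus one, divided by 365.25". The same section adds: "All participants will be censored on the date of their last observation". Neither the formula nor that sentence carries a week-48 cap, and the endpoint paragraph speaks of each patient's total duration of follow-up.

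**Which events count.** SAP 7.2.1: "For virological events only first episode was considered and data were censored at the time of treatment discontinuation". The Table 2B footnote: "All observed endpoint will be considered in the analysis".

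**Context.** SAP 3.1 and the study schedule place a visit 30 days after week 48. SAP 5.3 uses values from that visit, and SAP 10.2.3 describes viral load from week 48 to week 52. Protocol v5.0 section 6.5 keeps patients who stop study drug in follow-up to week 48. The data point set named for all secondary endpoints (DPS1, SAP 5.2.1) retains their observations.

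**The concern.** A person-time rate needs one risk period, shared by numerator and denominator. This rate lacks that in two respects.

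First, the methods section and the table shell end at different dates. The SAP does not define the end of the study, and data exist after week 48. Two programmers, each following the SAP, could report different rates, one of them including time after study drug has ended.

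Second, someone who stops study drug but stays in the study keeps adding person-years in which no virological event can count. That includes the week-48 viral load criterion, which is assessed only at the end. The same holds after a first virological episode. If stopping is unequal between arms, the diluted share of person-time is unequal too, and the incidence rate ratio moves for a reason other than risk of failure. Table 2B, read alone, would count those virological events, so the numerator also depends on which text is followed.

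**Working it through.** **The plan's own figure.** The documents state no value for this rate, so I use the design event count as an illustrative numerator. With 1:1 allocation, two-sided 5%, 80% power, margin 1.606 and expected hazard ratio 0.909 (SAP 4): events = 4 × (1.960 + 0.842)² / [ln(1.606/0.909)]² = 96.9, i.e. 97. This agrees with the SAP. Dividing by the mean failure probability, (0.25 + 0.23)/2 = 0.24, gives 403.8, i.e. 404 evaluable.

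**End date.** I use the SAP's formula, (days + 1)/365.25, and assume all 404 complete follow-up.

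- To week 48 (day 336): 337/365.25 = 0.923 person-years each, 372.8 in total; 97 events give 26.0 per 100 person-years.
- To the 30-day visit (day 366): 367/365.25 = 1.005 each, 405.9 in total; the same 97 events give 23.9 per 100.
- Extra person-time: 367/337 − 1 = 8.9%. Fall in the rate with no event in the added days: 1 − 337/367 = 8.2%. Both percentages are independent of the event count.
- The ±7-day visit windows put the extra person-time at about 7% to 11%.
- With equal follow-up in the two arms the factor cancels from the ratio.

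**Virological mismatch.** Inputs from SAP 4: clinical events 12.2% per year and virological failure 20% at week 48. I set true risk equal in both arms, so the true ratio is 1.00. Discontinuation rates and timing are assumptions. The ratio is the arm with more stopping over the arm with less.

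*Constant hazards.* Virological v = −ln(0.80)/(336/365.25) = 0.243 per person-year; clinical c = −ln(1 − 0.122) = 0.130. If a fraction d stops after a share t of follow-up and stays in the study, the observed rate is c + v × [1 − d(1 − t)]. For 5% v 15% and t = 0.25: (0.130 + 0.243 × 0.8875)/(0.130 + 0.243 × 0.9625) = 0.345/0.364 = 0.950.

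*Extreme case.* Every stopper loses all virological risk. With cumulative risks v = 0.10 to 0.20 and c = 0.122 × 336/365.25 = 0.112, the ratio is [(1 − d₂)v + c]/[(1 − d₁)v + c]. For 5% v 15% and v = 0.20: 0.282/0.302 = 0.934.

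| Assumed stopping | Constant hazards, t = 0.50 / 0.25 | Extreme, v = 0.10 / 0.15 / 0.20 |
|---|---|---|
| 5% v 10% | 0.983 / 0.975 | 0.976 / 0.971 / 0.967 |
| 5% v 15% | 0.967 / 0.950 | 0.952 / 0.941 / 0.934 |
| 5% v 20% | 0.950 / 0.925 | 0.928 / 0.912 / 0.901 |

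With equal stopping in the two arms the ratio is 1.00. Constant hazards understate the loss of the week-48 criterion, which any earlier stopper forfeits entirely; the extreme case overstates the loss of earlier events. Time after a first virological event is left out of both.

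**Offset from counted interruptions.** Component 2(d) of the primary endpoint counts adverse events or IRIS that interrupt therapy for more than 5 days. Let f be the share of stoppers counted that way (unknown; a switch within class inside 5 days is excluded). Adding f × d to each arm in the extreme case, with f = 0.25 and 5% v 15%:

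- v = 0.10: (0.085 + 0.112 + 0.0375)/(0.095 + 0.112 + 0.0125) = 0.2345/0.2195 = 1.07.
- v = 0.20: (0.170 + 0.112 + 0.0375)/(0.190 + 0.112 + 0.0125) = 0.3195/0.3145 = 1.02.

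The arm with more stopping then has the higher rate overall, although its later virological events are still lost.

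**The case against.** The end-date conflict may be no more than loose wording in a table shell: SAP 2.2.2 labels the endpoint at week 48, 7.2.1 names the week-48 visit, and SAP 3.1 describes a trial over 48 weeks. That is the likely intention. But nothing in the SAP says so, a later visit exists and is used elsewhere, and 7.2.1 itself computes time to an uncapped last observation. A reader might infer that the extra 30 days bias the treatment comparison; with equal follow-up they do not.

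A reader might infer that the Cox analysis of the composite avoids the virological mismatch. The documents do not support that. SAP 7.1 applies the same virological censoring at treatment discontinuation, and its list of reasons for ending follow-up does not include stopping drug. Someone off drug therefore stays in the composite risk set there as well. Only a model for the virological component alone would remove that time.

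A reader might also infer that the arm with more discontinuation gets a lower rate by construction. That does not follow either, because interruptions counted under 2(d) add events in the same arm and can reverse the net direction. The loss of virological events remains, but its net effect cannot be signed from the documents.

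It could be argued that censoring the virological data implies stopping virological person-time too. The section gives only one person-year formula, to last observation, and clinical events need that later time.

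**Conclusion.** The point stands as a defect in a secondary analysis that may not be run. Sections 7.2.1 and Table 2B give different end dates and different virological counting rules for one rate, and 7.2.1 divides truncated virological counts by untruncated person-time.

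The end date is worth up to 8.2% on the absolute rate and close to nothing on the ratio. The mismatch pulls the ratio in favour of the arm with more stopping by about 3-5% at an assumed 5% v 15%, with 7% as the upper bound at those rates. It vanishes if stopping is equal, and 2(d) events may offset or reverse it. All of this rests on assumed discontinuation rates and equal true risk. The non-inferiority conclusion does not depend on this analysis. It should be corrected before sign-off.

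**What to change.** - Table 2B footnote: replace both uses of *end of the study* with *the week-48 visit*.
- SAP 7.2.1: cap the last observation, and the total duration of follow-up, at that visit.
- State the same virological counting rule in 7.2.1 and in the Table 2B footnote.
- Keep the composite rate, and beside it report clinical and virological rates separately, with virological person-years ending at the first virological event or treatment discontinuation, whichever comes first.

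Dropping the cut at treatment discontinuation would also align numerator and denominator for off-drug time. It is less safe: virological events would then be counted differently from the primary analysis, and the 10-additional-event trigger would compare counts made under different rules.

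The cost is SAP wording and a few lines of code, with no new data. The downside is two extra rates to report. The SAP is at v0.3, and SAP 5.1 already provides for an update after the mock-up report and before sign-off.

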5. APPENDICES

APPENDIX 1 – AIDS-DEFINING CONDITIONS

From CDC, available at <https://www.cdc.gov/mmwr/preview/mmwrhtml/rr5710a2.htm>

- Bacterial infections, multiple or recurrent*
- Candidiasis of bronchi, trachea, or lungs
- Candidiasis of esophagus[†]
- Cervical cancer, invasive[§]
- Coccidioidomycosis, disseminated or extrapulmonary
- Cryptococcosis, extrapulmonary
- Cryptosporidiosis, chronic intestinal (>1 month's duration)
- Cytomegalovirus disease (other than liver, spleen, or nodes), onset at age >1 month
- Cytomegalovirus retinitis (with loss of vision)[†]
- Encephalopathy, HIV related
- Herpes simplex: chronic ulcers (>1 month's duration) or bronchitis, pneumonitis, or esophagitis (onset at age >1 month)
- Histoplasmosis, disseminated or extrapulmonary
- Isosporiasis, chronic intestinal (>1 month's duration)
- Kaposi sarcoma[†]
- Lymphoid interstitial pneumonia or pulmonary lymphoid hyperplasia complex*[†]
- Lymphoma, Burkitt (or equivalent term)
- Lymphoma, immunoblastic (or equivalent term)
- Lymphoma, primary, of brain
- *Mycobacterium avium* complex or *Mycobacterium kansasii*, disseminated or extrapulmonary[†]
- *Mycobacterium tuberculosis* of any site, pulmonary, ^{†§} disseminated, [†] or extrapulmonary[†]
- *Mycobacterium*, other species or unidentified species, disseminated[†] or extrapulmonary[†]
- *Pneumocystis jirovecii* pneumonia[†]
- Pneumonia, recurrent^{†§}
- Progressive multifocal leukoencephalopathy
- *Salmonella* septicemia, recurrent
- Toxoplasmosis of brain, onset at age >1 month[†]
- Wasting syndrome attributed to HIV

* Only among children aged <13 years. (CDC. 1994 Revised classification system for human immunodeficiency virus infection in children less than 13 years of age. MMWR 1994;43[No. RR-12].)

[†] Condition that might be diagnosed presumptively.

[§] Only among adults and adolescents aged ≥13 years. (CDC. 1993 Revised classification system for HIV infection and expanded surveillance case definition for AIDS among adolescents and adults. MMWR 1992;41[No. RR-17].)

APPENDIX 2 - INISIGHT SERIOUS NON-AIDS EVENTS CRITERIA

Version 4, August 2012

ACUTE MYOCARDIAL INFARCTION

- A. Rise and/or fall of cardiac biomarkers (preferably troponin), with at least one value above 99th percentile of upper reference limit (URL)
- B. Occurrence of a compatible clinical syndrome, including symptoms (such as chest pain) consistent with myocardial ischemia
- C. ECG changes indicative of new ischemia (new ST-changes or new left bundle branch block [LBBB]), or development of pathological Q waves on the ECG
- D. Imaging evidence of new loss of viable myocardium or new regional wall motion abnormality
- E. Sudden unexpected cardiac death involving cardiac arrest before biomarkers are obtained or before a time when biomarkers appear, along with (1) new ST-changes or new LBB, or (2) evidence of fresh thrombus on coronary angiography or at autopsy
- F. In patients with percutaneous coronary interventions and normal baseline troponin, increases in troponin of three times the 99th percentile of URL
- G. In patients with coronary artery bypass grafting and normal baseline troponin, increases in troponin of five times the 99th percentile of URL PLUS at least one of the following: (1) new pathological Q-waves or new LBBB, (2) angiographically documented new graft or native artery occlusion, or (3) imaging evidence of new loss of viable myocardium
- H. Pathologic findings of acute myocardial infarction (including acute MI demonstrated as the cause of death on autopsy)
- I. Development of 1) evolving new Q waves, or 2) evolving ST elevation, preferably based on at least 2 ECGs taken during the same hospital admission
- J. In patients with coronary artery bypass grafting and normal baseline troponin, increases in troponin of five times the 99th percentile of URL

Confirmed: One of the following 5 criteria (adapted from 2007 Universal Definition of Myocardial Infarction):

1. A + (B or C or D)
2. E
3. F
4. G
5. H

Probable: B+I or J

CONGESTIVE HEART FAILURE

- A. Clinical signs and symptoms compatible with left or right sided heart failure (e.g., paroxysmal nocturnal dyspnea, rales or S3 on auscultation, jugular venous distention) without an alternative explanation
- B. Hemodynamic measurements, radionuclide ventriculography, echocardiogram, cardiac catheterization, or multiple gated acquisition scan showing a decreased ejection fraction of < 45%

- C. Echocardiogram, cardiac catheterization or other studies showing evidence of increased left atrial pressure or right heart failure
- D. Elevated levels of Brain Natriuretic Peptide (BNP) or NT-proBNP
- E. Chest x-ray or other imaging study showing evidence of congestive heart failure, including cardiac enlargement
- F. Documentation of treatment for congestive heart failure

Confirmed: (A+B) or (A+C) or (A+D)

Probable: A+E+F

CORONARY ARTERY DISEASE REQUIRING DRUG TREATMENT

A written report in the medical record documenting:

- A. Evidence of myocardial ischemia based on either diagnostic imaging (such as a stress echocardiogram or thallium scan) or diagnostic changes on an electrocardiogram (such as during stress testing or an episode of chest pain)
- B. Evidence of coronary artery disease based on coronary angiography or other diagnostic imaging
- C. Other evidence of myocardial ischemia and/or coronary artery disease (including that based primarily upon symptoms and clinical presentation, such as chest pain with exertion)
- D. Use of medication given to treat or prevent angina (e.g., nitrates, beta blockers, calcium channel blockers)

Confirmed: (A or B) + D

Probable: C+D

CORONARY REVASCULARIZATION

Confirmed: A procedure report, hospital discharge summary, or other medical record from the hospitalization during which the procedure was performed for treatment of coronary artery disease (including coronary artery bypass graft, coronary artery stent implant, coronary atherectomy, and percutaneous transluminal angioplasty), or a consultation note from the participant's cardiologist documenting the occurrence of the procedure

Probable: Not applicable

DECOMPENSATED LIVER DISEASE

- A. Histologic, radiographic, or ultrasound evidence of cirrhosis, as documented by one of the following:
 1. Histologic evidence of cirrhosis obtained by liver biopsy or autopsy
 2. MRI or CT consistent with cirrhosis
 3. A positive result on transient elastography (FibroScan) or other ultrasound imaging consistent with cirrhosis

B. Clinical evidence of decompensation, as documented by one of the following, and without an alternative explanation:

1. Ascites
2. Hepatic encephalopathy
3. Bleeding from gastric or esophageal varices
4. Spontaneous bacterial peritonitis

Confirmed: A+B

Probable: B

DEEP VEIN THROMBOSIS

A. Diagnosis of deep vein thrombosis (DVT) by contrast venography, helical computed tomography, MRI, or ultrasonography other comparable imaging techniques

B. An elevated D-dimer test OR abnormal plethysmography

C. A score on the Wells Clinical Prediction Rule for DVT of ≥ 3 points

D. Absence of alternative diagnosis as likely or greater than that of deep venous thrombosis

Wells Clinical Prediction Rule for DVT

One point for each of the following:

- Active cancer (treatment ongoing or within previous 6 months, or palliative)
- Paralysis, paresis, or plaster immobilization of lower extremities
- Recently bedridden for more than 3 days, or major surgery, within 4 weeks
- Localized tenderness along distribution of the deep venous system
- Entire leg swollen
- Calf swelling by more than 3 cm when compared with the asymptomatic leg (measured 10 cm below tibial tuberosity)
- Pitting edema (greater in the symptomatic leg)
- Collateral superficial veins (non-varicose)

(Adapted from: Wells PS et al. Lancet 1997;350:1796)

Confirmed: A

Probable: B+C+D

DIABETES MELLITUS

A. Classic symptoms of hyperglycemia or hyperglycemic crisis plus a random plasma glucose concentration ≥ 200 mg/dl (11.1 mmol/l). (Classic symptoms include polyuria and polydipsia; Random is defined as any time of day without regard to last meal)

B. 2-hour plasma glucose ≥ 200 mg/dl (11.1 mmol/l) during an oral glucose tolerance test (The test should be performed using a glucose load containing the equivalent of 75 g anhydrous glucose dissolved in water).

C. Repeated abnormal fasting plasma glucose (FPG) and/or abnormal Haemoglobin A1C level (HA1C) results using the following criteria:

1. FPG ≥ 126 mg/dl (7.0 mmol/l) on at least two different dates (Fasting is defined as no caloric intake for at least 8 hours).

2. HA1C $\geq 6.5\%$ on at least two different dates
3. An FPG ≥ 126 mg/dl (7.0 mmol/l) PLUS a HA1C $\geq 6.5\%$, with these tests performed on two different dates

D. Documentation of taking an approved anti-diabetic medication to lower glucose levels in the blood, such as insulin or oral hypoglycaemic agents.

E. A single abnormal FBS OR a single abnormal HA1C

Confirmed: A or B or C

Probable: D

Possible: E

END-STAGE RENAL DISEASE

A. Haemodialysis or peritoneal dialysis documented in a clinical note for a period of at least three months

B. A kidney transplant documented in a clinical note

C. Haemodialysis or peritoneal dialysis documented in a clinical note for a period of at least one month and up to the time of death in a patient who dies within three months after dialysis begins

Confirmed: A or B

Probable: C

NON-AIDS-DEFINING CANCER

A. Diagnosis of cancer other than lymphoma, Kaposi's sarcoma (KS), or invasive cervical cancer in an autopsy report

B. Diagnosis of cancer other than lymphoma, KS, or invasive cervical cancer in a pathology report that established the diagnosis

C. Diagnosis of cancer other than lymphoma, KS, or invasive cervical cancer in a hospital discharge summary or consultation note from the hospitalization or clinic visit during which the diagnosis was established

Confirmed: A or B

Probable: C

PERIPHERAL ARTERIAL DISEASE

A. Compatible clinical signs and symptoms (e.g., intermittent claudication, femoral bruit, decreased peripheral pulses, change in colour or temperature of limb suggesting peripheral arterial disease)

B. Positive results on diagnostic imaging studies (e.g., Doppler ultrasound, contrast arteriography, MRI arteriography)

C. Ankle Brachial Pressure Index < 0.90 in non-diabetics

D. A procedure report, hospital discharge summary, or other medical record from the hospitalization during which the procedure was performed documenting an invasive procedure for treatment of peripheral arterial disease (e.g., percutaneous transluminal angioplasty, endovascular procedures, or vascular surgery), or a consultation note documenting the occurrence of the procedure

Confirmed: (A+B) or (A+C) or D

Probable: A

PULMONARY EMBOLISM

A. Symptoms compatible with pulmonary embolism, such as shortness of breath, chest pain, or haemoptysis

B. Results consistent with a diagnosis of pulmonary embolism on pulmonary angiography, helical CT, ventilation-perfusion scan or other comparable imaging studies

C. A diagnosis of pulmonary embolism on autopsy

D. Results consistent with a diagnosis of deep venous thrombosis on venography, ultrasound, or other comparable imaging studies

E. A chest x-ray which, if performed, does not suggest an alternative aetiology for the symptoms described in criteria A

Confirmed: (A+B) or C

Probable: A+D+E

STROKE

A. Acute onset with a clinically compatible course, including unequivocal objective findings of a localizing neurologic deficit

B. CT or MRI compatible with diagnosis of stroke and current neurologic signs and symptoms

C. Stroke diagnosed as cause of death at autopsy

D. Positive lumbar puncture compatible with subarachnoid haemorrhage

E. Death certificate or death note from medical record listing stroke as cause of death

Confirmed: (A+B) or C

Probable: (A+D) or (A+E)

